4. INVESTIGATIONAL PLAN

4.1 Overall Study Design

This study is a randomized, double-blind, placebo-controlled 15-week study of suvorexant for the treatment of insomnia in a cohort of 20 PD subjects between the ages of 30 and 80. Active drug will be suvorexant 10 mg at bedtime with an optional up-titration to 15 mg at bedtime after 2 weeks. Subjects will be enrolled based on a clinical history of insomnia as defined by the DSM-5 and on results of a screening PSG. The primary outcome measure will be change in sleep efficiency as measured on PSG. Participants will also receive a wearable sleep monitor to assess sleep efficiency over a longer period of time.

The study is composed of 5 office visits, 3 overnight sleep studies (PSGs), and up to 6 phone visits over the course of 11-15 weeks.

4.2 Enrollment

Subjects who may qualify for this study will be identified in the context of clinical care at the EvergreenHealth Neuroscience Institute or the EvergreenHealth Sleep Disorders Center. Such eligible patients may receive a copy of the informed consent form (ICF) at the time of their clinic visit. Recruitment may also occur through local promotional opportunities, referrals from other area neurologists, sleep medicine physicians, and the Washington State Parkinson Disease Registry. Patients may contact the EvergreenHealth Neuroscience Institute without clinic visitation after reading a notice about the study on the Institute's website or other online postings. Subjects who are not established patients at EvergreenHealth will be offered the chance to undergo a telephone screening using an institutional review board (IRB) approved telephone screening text. Subjects will be requested to send pertinent outside medical records for chart review by the principal investigator and be scheduled for a screening visit.

4.3 Screening

4.3.1 Office Visit 1

Office Visit 1 is the screening visit. At this clinic visit, subjects will provide written, informed consent. Once consent is provided, a unique identification number will be assigned. This will be the only identification number assigned to the subject for the duration of the study. After consent is obtained, subjects will be assessed for eligibility (excluding those eligibility criteria requiring completion of a PSG). A history of the patient's PD symptoms and sleep symptoms will be taken, and the patient's past medical history will be reviewed. Diagnosis of PD will be confirmed based on UK PD Society Brain Bank criteria (Hughes 1992). Current medication list will be reviewed, and a levodopa-equivalent daily dose will be calculated based on the patient's current PD medication list and on published conversion factors (Tomlinson 2010, Rytary Prescribing Information, Duopa Prescribing Information). Eligible subjects will have a stable PD medication regimen for 4 weeks prior to the screening visit and remain on a stable regimen for the duration

of the study. Eligible patients will also not be concomitantly taking any of the prohibited medications for at least 14 days prior to the screening visit. The patient's history of medication allergies will be reviewed.

Physical examination will be performed, both a general medical examination including vital signs (blood pressure, heart rate, and respiratory rate) and a neurological examination. Neurological exam will include a general neurological exam as well as MDS-UPDRS part 3 evaluation and modified Hoehn and Yahr (HY) staging of PD (Goetz 2004). Laboratory testing will include CBC, CMP, albumin, and INR, with calculation of the Child-Pugh score for any subjects with liver failure. Pre-menopausal women will have urine hCG measured. MoCA and the C-SSRS will be performed.

The wearable sleep monitor will be dispensed at Office Visit 1 to all subjects who meet non-PSG eligibility criteria. This will be worn by the subjects throughout the study and will record sleep efficiency on every night of the study. The wearable monitor will be the FitBit Charge, which is easy for subjects to put on and use, and provides automatic detection of sleep, calculating sleep duration and sleep efficiency. The FitBit Charge will be kept by the subjects as an honorarium for their time.

4.3.2 PSG 1

For all subjects who meet non-PSG eligibility criteria, the screening/baseline PSG will be completed within 3 weeks (0-21 days) after Office Visit 1. This will be performed at EvergreenHealth's Sleep Disorders Center according to their standard clinical protocol. At a minimum, PSG interpretation will report latency to persistent sleep (LPS), wakefulness after sleep onset (WASO), sleep efficiency, and apnea-hypopnea index (AHI). In addition to screening for eligibility, the screening PSG will provide baseline values for the PSG variables of interest. Eligibility will be confirmed based on the results of the PSG according to the eligibility criteria listed in section 5.1.

4.4 Treatment Period 1

4.4.1 Office Visit 2

For those who satisfy all eligibility criteria, Office Visit 2 will occur within 7-14 days after the screening PSG. Medications will be reviewed again to ensure stability of the PD medication regimen and absence of any prohibited medications.

Following confirmation of eligibility, an eligible patient will complete the baseline assessments of the MDS-UPDRS (only parts 1, 2, and 4; the data from part 3 that was collected at Office Visit 1 as a part of the screening will serve as the baseline for this measure), ISI, ESS, BDI, and BAI during Office Visit 2. Data from the wearable sleep monitor will be collected.

An eligible patient will be randomized in a 1:1 randomization scheme to receive suvorexant 10 mg qhs or placebo. Randomization will occur at the research pharmacy of EvergreenHealth using

a computer-generated randomization list. The pharmacist will maintain a codebook indicating the treatment allocation of each subject. Study medication will be delivered by the research pharmacist to the research study staff from the research pharmacy (a separate locked room containing only research medications). The investigating physicians, research coordinator(s), and study subjects will be blinded as to treatment arm until the code is broken. The randomization code may be broken by the investigator only in a medical emergency. The reasons for such an emergency will be documented carefully. The subjects will receive identical appearing active or placebo study medication tablets, with identification known only to the research pharmacist.

4.4.2 Phone Visit 1

Phone Visit 1 will occur 3-4 days after Office Visit 2 to review safety and tolerability through questioning about adverse events.

4.4.3 Phone Visit 2: Titration in Treatment Period 1

Phone Visit 2 will occur 2 weeks (12-15 days) after Office Visit 2 to review safety and tolerability through questioning about adverse events. The SGIC and C-SSRS will also be administered over the phone. Those subjects who report no AEs on suvorexant 10 mg po QHS (or matched placebo) and who report a persistent sleep disturbance will be titrated to suvorexant 15 mg po QHS (or matched placebo).

4.4.4 Phone Visit 3

Only for those subjects who are titrated to 15 mg, Phone Visit 3 will occur 3-4 days after Phone Visit 2 to review safety and tolerability through questioning about adverse events. For those who remain on 10 mg, Phone Visit 3 will not be conducted.

4.4.5 PSG 2

Overnight PSG 2 will occur after 4 weeks (25-32 days) after Office Visit 2 and will mark the last night of Treatment Period 1. Subjects will continue to take the study medication on the night of PSG 2. This will be performed at EvergreenHealth's sleep lab according to their standard clinical protocol. At a minimum, PSG interpretation will report latency to persistent sleep (LPS), wakefulness after sleep onset (WASO), and sleep efficiency.

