3.4 Secondary Hypotheses

1. On nights of PSG, total hours of sleep and WASO as measured by a wearable sleep monitor will not be significantly different from those values as measured by PSG.
2. Suvorexant will not worsen motor symptoms or non-motor symptoms of PD compared to placebo.

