5.1 Inclusion Criteria

An eligible subject:

- Has signed and dated an IRB-approved informed consent form before any protocol-specific screening procedures are performed;
- Has a diagnosis of Parkinson disease according to the United Kingdom Parkinson Disease Society Brain Bank Criteria (UKBB);
- Has a modified Hoehn and Yahr (mHY) Stage of 1-3, inclusive;
- Is aged 30-80 years old, inclusive;
- Has had no change in PD medications during the 4 weeks preceding screening, with no dose changes during the study, except that PRN (as needed) doses of carbidopa/levodopa will be allowed to address periodic worsening of parkinsonian symptoms;
- Is willing and able to complete PSG;
- Is willing and able to abstain from alcohol, caffeine, and marijuana for 6 hours prior to and during each study-related PSG;
- Is willing and able to abstain from products containing nicotine during each study-related PSG;
- Has Insomnia Disorder defined by diagnostic criteria published in the Diagnostic and Statistical Manual of Mental Disorders, 5th edition (DSM-5); namely, subject report of all of the following:
 - One of the following: difficulty initiating sleep; difficulty maintaining sleep; or early morning waking;
 - Sleep disturbance causes clinically significant distress or impairment in social, occupational, educational, academic, behavioral, or other important areas of functioning;
 - Sleep difficulty has occurred on 3 or more nights per week;
 - Sleep difficulty has been present for at least the past 3 months;
 - Sleep difficulty occurs despite adequate opportunity for sleep;
 - Insomnia is not explained by another sleep disorder;
 - Insomnia is not attributable to physiological effects of a consumed substance;
- On screening PSG, has a latency to persistent sleep \geq 20 minutes OR total wakefulness after sleep onset \geq 45 minutes;
- May use other medications that could influence sleep, other than those specifically prohibited, as long as the dose is stable for 4 weeks preceding screening, with no dose changes during the study; and

- Has valid health insurance coverage at the time of study enrollment and expects this coverage to remain valid for the duration of the study period.

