5.4 Removal of Patients from Study

A patient will be considered to have completed the study when he or she has completed all study visits through the final visit. Every patient has the right to discontinue study participation at any time at his/her own request, or may be withdrawn at any time at the discretion of the investigator for safety, behavioral, or administrative reasons. Criteria for early termination include, but are not limited to, poor adherence to study medication (less than 70% of study medication consumed), loss of health insurance coverage, and safety issues related to study-related or non-study related adverse events.

If a patient has a clinical necessity to alter their standard PD medications, the patient will be withdrawn from the trial so that changes may be made, except that occasional additional doses of carbidopa/levodopa will be allowed if needed to address periodic worsening of parkinsonian symptoms. If a patient is withdrawn due to an adverse event, the event will be followed, when possible, until resolution. Patients who withdraw from the study may be replaced, but withdrawn patients will not be re-entered into the study.

All data generated up to the time of discontinuation from the study will be analyzed and the reason(s) for discontinuation will be recorded.

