7.3.8 Movement Disorder Society's Unified Parkinson Disease Rating Scale (MDS-UPDRS)

The MDS-UPDRS is a widely used and validated (Goetz 2008) rating scale in PD, assessing non-motor symptoms of PD (part I), motor symptoms of PD (part II), motor signs of PD on physical exam (part III), and symptoms of motor complications in PD (part IV). Part I includes two questions about sleep symptoms: question 1.7 (sleep problems) and question 1.8 (daytime sleepiness). All questions are rated on a 5-point scale (0-4), with higher scores indicating greater severity. The maximum score on part I is 52, on part II it is 52, on part III it is 132, and on part IV it is 24. Total score, the score on part I, the score on question 1.7, and the score on question 1.8 will be secondary outcome measures. The scores on parts II, III, and IV will be used as safety measures to ensure no worsening of motor symptoms, motor signs, or motor complications. Part III will be performed at Office Visit 1; Parts I, II, and IV will be performed at Office Visit 2; and the full scale (parts I-IV) will be performed at Office Visits 3, 4, and 5.

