11. APPENDIX

11.1 Schedule of Assessments

Appendix 11.1: Schedule of Assessments

	Visit 1: Screening	PSG 1	Visit 2: Start Treatment Period 1	Phone Visit 1	Phone Visit 2	Phone Visit 3	PSG 2	Visit 3: Start Washout Period	Visit 4: Start Treatment Period 2	Phone Visit 4	Phone Visit 5	Phone Visit 6	PSG 3	Visit 5: Final
Timing	Week 0	Week 3 (0-21 days post Visit 1)	Week 5 (7-14 days post PSG 1)	Week 5.5 (3-4 days post Visit 2)	Week 7 (12-15 days post Visit 2)	Week 7.5 (3-4 days post Phone Visit 2)	Week 9 (25-32 days post Visit 2)	Week 9 (0-7 days after PSG 2)	Week 11 (11-18 days post Visit 3)	Week 11.5 (3-4 days post Visit 4)	Week 13 (12-15 days post Visit 4)	Week 13.5 (3-4 days post Phone Visit 5)	Week 15 (25-32 days post Visit 4)	Week 15 (0-7 days after PSG 3)
Informed Consent	X													
Study Eligibility (inclusion/exclusion)	X		X											
Medical History	X													
Sleep History	X													
PD History	X													
Concomitant Medication and Allergy Review	X		X					X	X					X
Levodopa-equivalent daily dose calculation	X													
AE Assessment				X	X	*		X	X	X	X	*		X
Physical Exam	X							X						X
MDS-UPDRS, Part 3 (Motor Exam)	X													
MDS-UPDRS, Parts 1, 2, & 4			X											
MDS-UPDRS, full assessment								X	X					X
UK Brain Bank Criteria review	X													
Hoehn and Yahr Staging for Parkinson's	X													
Laboratory Testing (CBC, CMP, albumin, INR)	X							X (CBC, CMP)	*					X (CBC, CMP)
Assessment of Child-Pugh Score	X													
Pregnancy Testing (urine hCG)	**		**					**	**					**
Overnight Polysomnogram (Sleep Study), including analysis by sleep specialist		X						X						X
Calculation of Sleep Efficiency		X						X						X
Calculation of Waking after Sleep Onset (WASO)		X						X						X
Calculation of Latency to Persistent Sleep		X						X						X
Insomnia Severity Index			X					X	X					X
Epworth Sleepiness Scale			X					X	X					X
Montreal Cognitive Assessment (MoCA)	X							X	X					X
Beck Depression Inventory			X					X	X					X
Beck Anxiety Inventory			X					X	X					X
Columbia Suicide Severity Rating Scale	X				X			X			X			X
Clinician's Global Impression of Change of disease symptoms								X	X					X
Subject's Global Impression of Change of disease symptoms					X			X	X		X			X
Dispense wearable sleep monitor	X													
Upload data from wearable sleep monitor			X					X	X					X
Randomization			X											
Drug Dispensing			X					X (placebo)	X					

*As indicated

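### Extra levodopa and withdrawals for PD-drug changes are not compared by treatment, so differential use could shrink the MDS-UPDRS motor contrast towards no worsening

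*Combined protocol and SAP*

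**What the plan says.** **Levodopa-equivalent daily dose (LEDD).** Section 4.3.1 states that at Office Visit 1 "a levodopa-equivalent daily dose will be calculated" from the current PD medication list. In Appendix 11.1 the row "Levodopa-equivalent daily dose calculation" is marked under Visit 1 only. The one stated use is a descriptive baseline summary (sections 1.11 and 8.4).

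**Extra levodopa.** Section 5.1 requires a stable PD regimen, "except that PRN (as needed) doses of carbidopa/levodopa will be allowed to address periodic worsening of parkinsonian symptoms". Section 5.4 likewise exempts such doses from its withdrawal rule: "occasional additional doses of carbidopa/levodopa will be allowed if needed to address periodic worsening of parkinsonian symptoms". No count or summary of these doses is described.

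**Withdrawal.** Section 5.4: "If a patient has a clinical necessity to alter their standard PD medications, the patient will be withdrawn from the trial". Withdrawn subjects may be replaced. Data up to discontinuation are analysed, and the reason is recorded.

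**Motor question.** Section 3.4 hypothesises: "Suvorexant will not worsen motor symptoms or non-motor symptoms of PD compared to placebo". Under section 7.3.8, the scores on MDS-UPDRS Parts II, III and IV "will be used as safety measures to ensure no worsening of motor symptoms, motor signs, or motor complications", and the total score is a secondary outcome. The full scale is scored at Office Visits 3, 4 and 5.

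**Analysis.** Section 8.5 compares outcomes by ANCOVA or another method chosen by the statistician. It names no covariates and mentions neither extra levodopa nor withdrawals for PD-drug change.

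**The concern.** The as-needed allowance treats the symptoms and signs that MDS-UPDRS Parts II to IV are meant to detect. If suvorexant makes them worse, subjects may take more levodopa in the suvorexant period than in the placebo period. The score then reflects suvorexant plus the additional levodopa, and the difference between treatments is smaller than the effect of suvorexant itself.

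Withdrawal is a second route. A subject whose worsening calls for a regimen change leaves the trial, possibly before any on-treatment motor score exists, and may be replaced.

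For a superiority hypothesis, attenuation of this kind would be conservative. Here the hypothesis is that there is no worsening, so attenuation of a real harm favours the hoped-for conclusion. At stake is the motor safety statement that a later, larger trial might inherit.

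**Working it through.** The plan states no effect size, standard deviation, margin or power for the motor question, so it has no figure to reproduce. The check sets the sections side by side and then illustrates sensitivity under stated assumptions.

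**Step 1. Could the plan detect differential levodopa use?**
- LEDD is calculated once, before randomisation (section 4.3.1, Appendix 11.1), so it cannot differ by treatment received.
- Medications are reviewed again at Office Visits 2 to 5. The stated purpose is to confirm regimen stability and the absence of prohibited drugs (sections 4.4.1, 4.5, 4.6.1, 4.7). Counting as-needed doses is not mentioned.
- Section 6.3 requires all concomitant therapy to be documented. As-needed doses may therefore be on file, but no dose total or comparison is planned.
- The ON state is named only for the baseline Part III summary (section 8.4). No medication state or time since last levodopa is specified for Office Visits 3 to 5, so a recent extra dose could affect a score without being noticed.

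**Step 2. What can mask worsening, and what cannot?**
- An increase in the standard regimen cannot mask worsening in a continuing subject, because it leads to withdrawal (section 5.4). In continuing subjects, LEDD can depart from its screening value only through as-needed doses.
- A withdrawn subject contributes a missing later score, not a zero change. Appendix 11.1 schedules no MDS-UPDRS at early termination, and section 4.8 does not list it for unscheduled visits.

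**Step 3. Direction.** As-needed levodopa is available in both periods. Differential use shrinks a true difference of either sign. It favours a finding of no worsening only if suvorexant does worsen motor function.

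**Step 4. Illustration only.** Assumptions: 20 completers (section 8.2), two-sided 0.05 (section 8.5), within-subject comparison with 18 degrees of freedom, and effects in units of the SD of the within-subject treatment difference. The share of worsening offset by extra levodopa is also assumed, because the documents give no amounts.

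Power = P(noncentral t with 18 df and noncentrality d × √20 exceeds 2.101), where √20 = 4.472.

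- No offset: d = 0.662, noncentrality 0.662 × 4.472 = 2.96, power 80%. The normal approximation needs d = (1.960 + 0.842) / 4.472 = 0.63.
- 25% offset: d = 0.497, noncentrality 2.22, power about 56%.
- 50% offset: d = 0.331, noncentrality 1.48, power about 29%.
- 75% offset: d = 0.166, noncentrality 0.74, power about 10%.

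The 95% confidence half-width is 2.101 / 4.472 = 0.47 SD. A non-significant motor result would be weak evidence of no worsening even with no masking at all.

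**The case against.** The strongest reply is that treated worsening is not lost to the trial. Section 7.1.4 counts worsening of a condition present at screening as an adverse event, graded and rated for relatedness under blind. Adverse events are assessed at the scheduled phone visits and at Office Visits 3, 4 and 5, and they form part of the primary hypothesis. Concomitant therapy is documented and reasons for discontinuation are recorded. All of this stands. It means that worsening may be muted in the MDS-UPDRS contrast, and a reader who infers that it would be invisible goes further than the documents allow. What remains is that none of these sources is tied to the motor comparison or tabulated by treatment for this purpose.

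Three other inferences are tempting and should be resisted.
- That the single LEDD calculation causes the masking. The as-needed allowance permits it. A repeated LEDD would only show it.
- That every withdrawal for a PD-drug change is motor worsening. Section 5.4 covers any clinical need to alter PD drugs and does not limit the reason.
- That a bias in MDS-UPDRS points can be quoted. The documents give no frequency or size of masked worsening, and section 5.4 describes the permitted extra doses as occasional.

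It is also fair to say that the study is an exploratory pilot of 20 subjects, that Parts II to IV are safety measures, and that the hypothesis has no margin. These facts limit the severity of the point but do not answer it.

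**Conclusion.** The point holds as a minor one with a cheap improvement. The plan allows extra levodopa for the worsening that it seeks to rule out, removes subjects who need a regimen change, and compares neither by treatment. A conclusion of no motor worsening would therefore be open to confounding by differential levodopa use or withdrawal.

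The bias arises only if suvorexant worsens motor function and extra dosing or withdrawal then differs between treatments. Its size cannot be computed from the documents, and the power figures above depend on assumed offset shares. It concerns the second secondary hypothesis and motor safety. The documents give no ground for extending it to the primary endpoint, sleep efficiency on PSG.

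**What to change.** 1. At the medication reviews already scheduled at Office Visits 3 and 5, record the as-needed carbidopa/levodopa taken during the treatment period just ended, with dose and dates. Dates matter because each visit may fall up to 7 days after the PSG that closes the period (sections 4.5 and 4.7).
2. Calculate LEDD including these doses for each treatment period. Compare it within subject between suvorexant and placebo, and interpret MDS-UPDRS Parts II to IV and the total score alongside it. Treat it as an outcome and not as an ANCOVA covariate, since it may itself be affected by treatment.
3. Tabulate withdrawals for PD-medication change by the treatment being taken at the time. In a sensitivity analysis, count as motor worsening only those whose recorded reason is motor worsening.

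The cost is a few extra data fields, two LEDD calculations per subject and one added table, with some recall error in the as-needed counts. The change reveals masking but does not prevent it. The as-needed and withdrawal rules stay as written.

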4.5 Washout Period (Office Visit 3)

Office Visit 3 will occur within 7 days after PSG 2. In addition to PSG review, medications will be reviewed again to ensure stability of the PD medication regimen and absence of any prohibited medications. Any possible adverse events (AEs) will be assessed. General physical exam will be performed, including vital signs (blood pressure, heart rate, and respiratory rate).

PD symptoms and signs will be assessed with the complete MDS-UPDRS. Study scales (MoCA, ISI, ESS, BDI, BAI, CGI-C, SGI-C, C-SSRS) will be administered. Data from the wearable

sleep monitor will be collected. Laboratory testing will be performed as deemed appropriate by the investigator.

A new supply of study pills will be dispensed. For the washout period, all subjects will be given the placebo matching the dose being administered most recently (i.e. in the second half of treatment period 1).

4.6 Treatment Period 2

4.6.1 Office Visit 4

Office Visit 4 will occur 2 weeks (11-18 days) after Office Visit 3 and will mark the beginning of treatment period 2. Medications will be reviewed again to ensure stability of the PD medication regimen and absence of any prohibited medications. Any possible adverse events (AEs) will be assessed.

To serve as baseline scores for treatment period 2, PD symptoms and signs will be assessed with the complete MDS-UPDRS and study scales (MoCA, ISI, ESS, BDI, BAI, CGI-C, SGI-C) will be administered. Data from the wearable sleep monitor will be collected. Laboratory testing, including urine hCG, will be performed as deemed appropriate by the investigator.

A new supply of study pills will be dispensed in a crossover fashion. All subjects who received study drug in treatment period 1 will be given placebo in treatment period 2, and all subjects who received placebo in treatment period 1 will be given study drug in treatment period 2. For treatment period 2, double-blinding will be resumed. Initial dose for all subjects will be 10 mg qhs.

4.6.2 Phone Visit 4

Phone Visit 4 will occur 3-4 days after Office Visit 4 to review safety and tolerability through questioning about adverse events.

4.6.3 Phone Visit 5: Titration in Treatment Period 2

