Phone Visit 5 will occur 2 weeks (12-15 days) after Office Visit 4 to review safety and tolerability through questioning about adverse events. The SGIC and C-SSRS will also be administered over the phone. Those subjects who report no AEs on suvorexant 10 mg po QHS (or matched placebo) and who report a persistent sleep disturbance will be titrated to suvorexant 15 mg po QHS (or matched placebo).

4.6.4 Phone Visit 6

Only for those subjects who are titrated to 15 mg, Phone Visit 6 will occur 3-4 days after Phone Visit 5 to review safety and tolerability through questioning about adverse events. For those who remain on 10 mg, Phone Visit 6 will not be conducted.

4.6.5 PSG 3

PSG 3 will occur 4 weeks (25-32 days) after Office Visit 4 and will mark the last night of Treatment Period 2. Subjects will continue to take the study medication on the night of PSG 3. This will be performed at EvergreenHealth's sleep lab according to their standard clinical protocol. At a minimum, PSG interpretation will report latency to persistent sleep (LPS), wakefulness after sleep onset (WASO), and sleep efficiency.

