4.7 Final Visit (Office Visit 5)

Office Visit 5 will occur within 7 days after PSG 3. Medications will be reviewed again to ensure stability of the PD medication regimen and absence of any prohibited medications. Any possible adverse events (AEs) will be assessed. General physical exam will be performed, including vital signs (blood pressure, heart rate, and respiratory rate).

PD symptoms and signs will be assessed with the MDS-UPDRS and study scales (MoCA, ISI, ESS, BDI, BAI, CGI-C, SGI-C, C-SSRS) will be administered. Data from the wearable sleep monitor will be collected. Laboratory studies will be performed (CBC, CMP). Pregnancy testing with urine hCG will be performed if deemed appropriate by the investigator.

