5.3 Prohibited Medications

The following medications are not permitted to be used within 14 days prior to screening nor for the duration of the subject's participation in the study:

- Digoxin;
- CNS depressants such as:
 - Benzodiazepines
 - Alprazolam
 - Chlorazepate
 - Chlordiazepoxide
 - Clonazepam
 - Diazepam
 - Estazolam
 - Flurazepam
 - Halazepam
 - Lorazepam
 - Midazolam
 - Oxazepam
 - Prazepam
 - Temazepam
 - Triazolam
 - Barbiturates
 - Amobarbital
 - Mephobarbital
 - Pentobarbital
 - Phenobarbital
 - Primidone
 - Secobarbital
 - Sodium thiopental
 - Opiates
 - Codeine
 - Hydrocodone
 - Hydromorphone
 - Methadone
 - Morphine
 - Oxycodone
 - Zolpidem
 - Zaleplon
 - Eszopiclone
- Moderate or strong inhibitors of CYP3A, such as:
 - Aprepitant
 - Atazanavir
 - Bromocriptine

- Chloramphenicol
- Ciprofloxacin
- Clarithromycin
- Cobicistat
- Conivaptan
- Darunavir
- Desipramine
- Diltiazem
- Dronedarone
- Erythromycin
- Felodipine
- Fluconazole
- Fluvoxamine
- Fosamprenavir
- Grapefruit Juice
- Imatinib
- Indinavir
- Itraconazole
- Ketoconazole
- Lopinavir
- Nefazadone
- Nelfinavir
- Nicardipine
- Posaconazole
- Quinidine
- Quinupristin
- Ritonavir
- Saquinavir
- Telaprevir
- Telithromycin
- Verapamil
- Voriconazole
- Strong inducers of CYP3A, such as:
 - Carbamazepine
 - Dexamethasone
 - Phenobarbital
 - Primidone
 - Phenytoin
 - Rifampin
 - St. John's Wort

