6. TREATMENTS

6.1 Investigational Drug

Study medication, to include 5-mg and 10-mg suvorexant and matching placebo, will be provided by Merck. The active medication will be suvorexant 10-15 mg qhs. The research pharmacist at EvergreenHealth will be responsible for packaging and labeling individual bottles, which will be done in a standard prescription bottle with child-proof cap. The pharmacist will dispense the active or placebo medication at randomization (Office Visit 2, start of Treatment Period 1) and again Office Visit 4 (start of Treatment Period 2). This will include a 4-week supply of 10 mg tablets (suvorexant or matching placebo) and a 2-week supply of 5 mg tablets (suvorexant or matching placebo). The subject will use the 5-mg tablets only if instructed to do so at Phone Visit 2 or Phone Visit 5. In this case, the 5-mg tablets will be taken concurrently with the 10-mg tablets to achieve the titration dose of 15 mg QHS. To prevent confusion, the bottle of 5-mg tablets will be packaged in a sealed bag with a label stating, "Open only if instructed to do so on _____." In the blank, the coordinator will write in the date of Phone Visit 2 or 5, as appropriate. In addition, a pictorial depiction of the titration schedule will be provided to the subject.

At Office Visit 3 (start of washout period), placebo will be dispensed that matches what the subject was taking at the end of Treatment Period 1. For example, if the subject titrated to 15 mg at Phone Visit 2, both a 10-mg and 5-mg placebo will be dispensed at Office Visit 3. If the subject remained on 10 mg for the duration of Treatment Period 1, only a 10-mg placebo will be dispensed.

An extra 7-day supply of medication will be provided for each study period to allow a window for scheduling of appointments.

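### No scheduled check for section 5.3 drugs takes place at Phone Visits 2 and 5, where the dose may rise from 10 to 15 mg

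*Combined protocol and SAP*

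**What the plan says.** **The ban.** Section 5.3 lists drugs that are "not permitted to be used within 14 days prior to screening nor for the duration of the subject's participation". The list covers digoxin, CNS depressants, moderate or strong CYP3A inhibitors and strong CYP3A inducers. Section 6.3 adds that all concomitant therapy is to be documented, without saying when, and that drugs likely to influence sleep may not be started during the study.

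**When it is checked.** The medication list is reviewed at Office Visit 1 (4.3.1). At Office Visit 2, when drug is first dispensed, section 4.4.1 says: "Medications will be reviewed again to ensure stability of the PD medication regimen and absence of any prohibited medications". Section 4.6.1 requires the same at Office Visit 4, the second dispensing visit. For Office Visit 3, section 4.5 says: "In addition to PSG review, medications will be reviewed again to ensure stability of the PD medication regimen and absence of any prohibited medications". Office Visit 5 repeats the review (4.7).

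**The titration calls.** Section 4.4.3: "Phone Visit 2 will occur 2 weeks (12-15 days) after Office Visit 2 to review safety and tolerability through questioning about adverse events". Section 4.6.3: "Phone Visit 5 will occur 2 weeks (12-15 days) after Office Visit 4 to review safety and tolerability through questioning about adverse events". Each call also includes the SGIC and the C-SSRS. Subjects with no reported adverse event on 10 mg (or matching placebo) "who report a persistent sleep disturbance will be titrated to suvorexant 15 mg po QHS (or matched placebo".

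**Release of the extra tablet.** The 5-mg tablets are handed out in a sealed bag at Office Visits 2 and 4. Section 6.1: "The subject will use the 5-mg tablets only if instructed to do so at Phone Visit 2 or Phone Visit 5".

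**The concern.** The protocol does not rely on the ban alone: at every office visit from the second onward it checks that no prohibited drug is in use. The titration call is the one step at which exposure is deliberately increased, and it has no such check. The subject already holds the 5-mg tablets, so the call is the only gate between 10 and 15 mg.

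The titration rule selects subjects who still sleep badly. It is reasonable to infer, though the documents give no rate, that some of them might try another sleep aid. Section 5.3 also includes items that a subject may not think to mention when asked about adverse events, such as grapefruit juice, diltiazem or verapamil.

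What is at stake is safety. Section 2.2 restricts the study to 10 and 15 mg because people with PD may be more sensitive to suvorexant and are likely to take other drugs that add to daytime somnolence. Raising the dose on top of an undetected CNS depressant or CYP3A inhibitor works against that caution.

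**Working it through.** The plan states no figure for this gap, so there is none to reproduce. The check compares the visit texts and adds up the visit windows.

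**Scheduled medication reviews.** Sections 4.3.1, 4.4.1, 4.5, 4.6.1 and 4.7 place a review at Office Visits 1 to 5. Schedule 11.1 agrees: the concomitant medication row is marked at Visits 1, 2, 3, 4 and 5 and is blank at all six phone visits. The phone columns can be trusted, because the C-SSRS row marks Phone Visits 2 and 5, as section 7.3.9 says it should. The PSG columns are not used here.

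**Contacts between dispensing and titration.** The only one is Phone Visit 1 or 4 on day 3-4, described as adverse event questioning (4.4.2, 4.6.2).

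**Inputs**, in days from dispensing (Office Visit 2 or 4) unless stated:
- Titration call: 12-15 (4.4.3, 4.6.3).
- PSG, the last treatment night: 25-32 (4.4.5, 4.6.5).
- Next office visit: 0-7 days after the PSG (4.5 and 4.7; for the second period, "Office Visit 5 will occur within 7 days after PSG 3").
- Post-titration call: 3-4 days after the titration call (4.4.4, 4.6.4).

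**Results**, the same in both periods:
- Last scheduled review to titration call: 12-15 days.
- Dispensing to next scheduled review: 25 + 0 = 25 to 32 + 7 = 39 days.
- Titration call to next scheduled review: 25 - 15 + 0 = 10 to 32 - 12 + 7 = 27 days.
- Nights at 15 mg up to and including the PSG night, if the extra tablet starts on the night of the call: 25 - 15 + 1 = 11 to 32 - 12 + 1 = 21.
- Post-titration adverse event call: 12 + 3 = 15 to 15 + 4 = 19 days after dispensing.
- Dose increase: 5/10 = 50%.

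**Decisions exposed.** Each subject who completes both periods has one titration decision on active drug, so about 20 in all. These are decisions, not titrations: a subject with an adverse event, or whose sleep has improved, stays on 10 mg. In the placebo period the added tablet is placebo and the concern does not arise.

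The next scheduled review follows the PSG that ends the period. It can record use of a banned drug but cannot prevent the increase.

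**The case against.** The strongest reply is that the ban already governs the titration step. Sections 4.4.3 and 4.6.3 operate within sections 5.3 and 6.3 and need not restate them, and section 5.4 lets the investigator withdraw a subject at any time for safety. Medications are reviewed on the dispensing day itself, so the window opens with a check. The call also tests for the harm in question. Section 7.1.4 requires specific questions about falls and next-day drowsiness, counts any new symptom or illness as an adverse event whatever its cause, and any reported adverse event blocks titration. A further adverse event call follows 3-4 days later, unscheduled visits include a medication review (4.8), and 15 mg is below the approved 20 mg. The proposed question is itself self-report and would not catch every case.

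Most of this stands, and it narrows the point. A reader might infer that the protocol permits section 5.3 drugs during treatment or at titration. It does not: such a subject is already in breach at 10 mg. What remains is undetected use, begun or undisclosed since dispensing, in a subject with no reported adverse event and continuing poor sleep. The safeguards listed look for symptoms, depend on an unplanned visit, or cap the dose. None schedules a question about drugs before the dose rises. That self-report is imperfect is no reason to leave the question out.

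A reader might also extend the over-exposure argument to every drug in section 5.3. It does not fit strong CYP3A inducers, which give no reason to fear excess exposure when the dose is raised. The argument here is confined to CNS depressants and moderate or strong CYP3A inhibitors.

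**Conclusion.** The point holds as a minor safety improvement. Section 5.3 drugs are banned throughout and checked at dispensing, but no scheduled check takes place 12-15 days later, when the dose may rise by 50%. The next scheduled review is 10-27 days after that, once treatment in the period has ended.

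This rests on the visit windows as written, on the extra tablet starting on the night of the call (for the count of 11-21 nights), and on staff following the stated call content without adding a medication question of their own. The documents give no rate of prohibited-drug use, so the number of affected subjects cannot be estimated. It could be zero.

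A reader might go on to infer that the comparison of sleep efficiency is biased. The documents give no basis for that, and it is not claimed. No sample size, test or significance level is affected.

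**What to change.** - At Phone Visits 2 and 5, ask about section 5.3 drugs before giving the titration instruction. Ask in the same way in both periods, so that the blind is untouched.
- Add a third condition to 4.4.3 and 4.6.3: a subject using a section 5.3 drug is not titrated, and whether the subject continues is decided under section 5.4. Using the whole list keeps the question simple; inducers are covered because they are banned, not because of over-exposure.
- Mark concomitant medication review in the Phone Visit 2 and Phone Visit 5 columns of schedule 11.1.

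The cost is one short question at two calls that already take place, or 2 x 20 = 40 questions for 20 subjects, one clause in each of two sections, and two marks in the schedule. No new visit, procedure or unblinding is needed. The downside is a few withheld titrations or additional recorded deviations.
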